2. SCHEDULE OF ASSESSMENTS

The schedule of assessments is provided in [Table 1](#) for Part A (single dose administration) and [Table 2](#) for Part B (multiple dose administration).

Table 1: Schedule of Assessments - Part A (Single Dose Administration)

Assessment	Screening	Admission	Confinement				Follow-up (14-16 days after dosing day)
	Study Day						
Assessment	-28 to -2	-1	1	2	3	4	15-17
Admission ^a		X					
Randomization			X				
Confinement		X	X	X	X	X	
Discharge ^b						X	
Outpatient Visit	X						X
Informed Consent ^c	X						
Inclusion and Exclusion Criteria Check	X	X					
Demographics	X						
Medical History	X						
Smoking Screen (cotinine urine test)	X	X					
Drugs of Abuse (urine)/Alcohol Screen (urine and breath) ^d	X	X					

Assessment	Screening	Admission	Confinement				Follow-up (14-16 days after dosing day)
	Study Day						
Assessment	-28 to -2	-1	1	2	3	4	15-17
Physical Examination ^e	X ^e	X				X	X
Prior and Concomitant Medication	Details for all medications will be taken on an ongoing basis from screening to follow-up (FU).						
Height, weight, and BMI ^f	X						X ^f
Vital Signs ^g	X	X	X ^g	X	X	X	X
Peak Expiratory Flow Rate ^h		X	X ^h	X			X
Safety Single 12-Lead ECG	X	X			X	X	X
Extensive Triplicate ECG ⁱ			X ⁱ	X			
Serology Tests (HBsAg, HCV Ab, HIVAg and Ab)	X						
Hematology, Coagulation, and Clinical Chemistry ^j	X	X		X		X	X
Urinalysis ^j	X	X					X

Assessment	Screening	Admission	Confinement				Follow-up (14-16 days after dosing day)
	Study Day						
Assessment	-28 to -2	-1	1	2	3	4	15-17
Alpha-1-acid Glycoprotein	X						
Total, LDL, and HDL Cholesterol	X						
FSH test – Females only ^k	X						
Pregnancy Test- Females only ^l	X	X					
PK Sampling – Plasma ^m			XError! Reference source not found.	XError! Reference source not found.	XError! Reference source not found.	X	
PK Sampling – Urine ⁿ			XError! Reference source not found.	XError! Reference source not found.	XError! Reference source not found.	X	
PGX Sampling – Whole blood ^o		X					
Study Drug Dosing ^p			X				

Assessment	Screening	Admission	Confinement				Follow-up (14-16 days after dosing day)
	Study Day						
Assessment	-28 to -2	-1	1	2	3	4	15-17
Adverse Event Assessment and Reporting	Ongoing from the time of signing the Informed Consent Form (Non-treatment and Treatment emergent adverse events)						

^a Subjects will be admitted to the clinic the day prior to study drug administration.

^b Subjects will be discharged on Study Day 4 after the 72-hour PK sample has been collected and the final assessment has been completed.

^c At screening, a separate informed consent form (ICF) will be used to obtain the subject's consent for the utilization of their DNA for pharmacogenomic (PGX) testing.

^d For drugs of abuse/alcohol screen, refer to Section 10.6.2. At the time of signing the ICF, a negative result from the breath alcohol test is required.

^e Complete physical examination should be performed at screening only. Abbreviated physical examination should be performed at all other marked study days. See Section 10.6.3.

^f Height and weight will be collected, and BMI calculated at screening. Only weight will be collected at FU.

^g Highlighted time points for vital signs (Section 10.6.3) as follows: pre-dose (baseline), 1, 2, 3, 4, 6, 8, and 12 hours post-dose on Day 1. Vital signs should be assessed at all other marked study days.

^h Peak expiratory flow rate will be assessed at admission (Day -1), pre-dose (baseline), 2 and 24 hours post-dose after the single dose, and FU.

ⁱ Extensive triplicate ECGs, except for the food effect cohort, will be obtained to collect continuous 12-lead ECG data from pre-dose until 24 hours post-dose as specified. Three replicates (triplicate) of ECG data will be collected as close as possible from -0.75, -0.5, and -0.25 hours pre-dose and 0.5, 1, 2, 3, 4, 6, 8, 12, and 24 hours post-dose after single dose administration. Subjects should not eat a meal within 1 hour of digital ECG data collection. See the instruction on lunch and dinner time (Section 8.3.1) to avoid any meal intake within 1 hour of the 6-hour and 12-hour post-dose ECG time points.

^j For clinical laboratory assessments, refer to Section 10.6.2.

^k Postmenopausal status for females of non-childbearing potential will be further confirmed with the follicle-stimulating hormone (FSH) serum levels that are consistent with postmenopausal status. Refer to Inclusion Criteria for details (Section 8.1).

^l Pregnancy test (serum) will be collected at screening and admission (Day -1) to confirm pregnancy status of the gender effect cohort (Section 8.1).

^m PK blood draw will be performed at pre-dose and 0.25, 0.5, 1, 2, 3, 4, 6, 8, 10, 12, 16, 18, 24, 36, 48, 60, and 72 hours post-dose following the single dose administration (Section 10.3.1). See Table 8 for PK time window.

ⁿ PK urine samples, except for the food and gender effect cohorts, will be collected for each specified time interval: pre-dose and between 0-4, 4-8, 8-12, 12-24, 24-48, and 48-72 hours post-dose following the single dose administration (Section 10.3.2). The urine volume at each interval should be recorded as part of PK data.

^o PGX samples (whole blood) will only be collected from the subjects who consented for DNA testing.

^p Details regarding study drug administration are provided in Section 9.3.

BMI: body mass index; ECG: electrocardiogram; FSH: following-stimulating hormone; FU: Follow-up; HbsAg: hepatitis B surface antigen; HCV Ab: hepatitis C antibody; HDL: high density lipoprotein; HIV Ab: human immunodeficiency virus antibody; ICF: informed consent form; LDL: low density lipoprotein; PK: pharmacokinetic(s); PGX: pharmacogenomic(s).

Table 2: Schedule of Assessments - Part B (Multiple Dose Administration)

Assessment	Screening	Admission	Confinement															Follow-up (14 – 16 days after final dosing day)		
	Study Day																			
Assessment	-28 to -2	-1	1	2	3	4	5	6	7	8	9	10	11	12	13	14	15	16	17	28 to 30
Admission ^a		X																		
Randomization			X																	
Confinement		X	X	X	X	X	X	X	X	X	X	X	X	X	X	X	X	X	X	
Discharge ^b																				X
Outpatient Visit	X																			X
Informed Consent ^c	X																			
Inclusion and Exclusion Criteria Check	X	X																		
Demographics	X																			
Medical History	X																			
Smoking Screen (cotinine urine test)	X	X																		
Drugs of Abuse (urine)/Alcohol Screen (urine and breath) ^d	X	X																		

Assessment	Screening	Admission	Confinement																Follow-up (14 – 16 days after final dosing day)		
	Study Day																				
Assessment	-28 to -2	-1	1	2	3	4	5	6	7	8	9	10	11	12	13	14	15	16	17	28 to 30	
Physical Examination ^e	X ^e	X																	X	X	
Prior and Concomitant Medication	Details for all medications will be taken on an ongoing basis from screening to follow-up (FU).																				
Height, Weight, and BMI ^f	X																			X ^f	
Vital Signs ^g	X	X	X ^g	X	X	X															
Peak Expiratory Flow Rate ^h		X	X ^h	X														X ^h	X		X
Safety Single 12-lead ECG	X	X																	X	X	X
Extensive Triplicate ECG ⁱ			X ⁱ	X	X	X	X	X	X	X	X	X	X	X	X	X	X ⁱ	X			
Serology Tests (HBsAg, HCV Ab, HIVAg and Ab)	X																				
Hematology, Coagulation, and Clinical Chemistry ^j	X	X			X				X								X		X		X

Assessment	Screening	Admission	Confinement																Follow-up (14 – 16 days after final dosing day)	
	Study Day																			
Assessment	-28 to -2	-1	1	2	3	4	5	6	7	8	9	10	11	12	13	14	15	16	17	28 to 30
Urinalysis ^j	X	X			X					X							X		X	X
Alpha-1-acid Glycoprotein	X																			
Total, LDL, and HDL Cholesterol	X																X		X	
C-SSRS	X																X			X
PK Sampling – Plasma ^k			X ^k	X	X	X	X	X	X ^k	X	X	X	X	X	X	X ^k	X ^k	X ^k	X	
PGX Sampling – Whole blood ^l		X																		
Study Drug Dosing ^m			X	X	X	X	X	X	X	X	X	X	X	X	X					
Adverse Event Assessment and Reporting	Ongoing from the time of signing the Informed Consent Form (Non-treatment and Treatment emergent adverse events)																			

^a Subjects will be admitted to the clinic the day prior to study drug administration.

^b Subjects will be discharged on Study Day 17, after the 72-hour PK sample from the final dose has been collected and the final assessment has been completed.

^c At screening, a separate informed consent form (ICF) will be used to obtain the subject's consent for the utilization of their DNA for pharmacogenomic (PGX) testing.

^d For drugs of abuse/alcohol screen, refer to Section 10.6.2. At the time of signing the ICF, a negative result from the breath alcohol test is required.

^e Complete physical examination should be performed at screening only. Abbreviated physical examination should be performed at all other marked study days. See Section 10.6.3.

^f Height and weight will be collected, and BMI calculated at screening. Only weight will be collected at FU.

^g Highlighted time points for vital signs (Section 10.6.3) as follows: pre-dose (baseline), 1, 2, 3, 4, 6, 8, and 12 hours post-dose on Day 1; pre-dose, and at 2, 6, and 8 hours post-dose on Days 2 through 14. Vital signs should be assessed at all other marked study days.

^h Peak expiratory flow rate will be assessed at admission (Day -1), pre-dose (baseline), 2 and 24 hours post-dose after the first dose (Day 1 dosing) and the last dose (Day 14 dosing), and FU.

ⁱ Extensive triplicate ECGs will be obtained to collect continuous 12-lead ECG data from pre-dose until 24 hours post-dose as specified. Three replicates (triplicate) of ECG data will be collected as close as possible from -0.75, -0.5, and -0.25 hours pre-dose, and 0.5, 1, 2, 3, 4, 6, and 8 hours post-dose on Day 1, at pre-dose only on Days 2 through 13, and -0.75, -0.5, and -0.25 hours pre-dose and 0.5, 1, 2, 3, 4, 6, 8, 12, and 24 hours post-dose on Day 14. Subjects should not eat a meal within 1 hour of digital ECG data collection. See the instruction on lunch and dinner time (Section 8.3.1) to avoid any meal intake within 1 hour of the 6-hour and 12-hour post-dose ECG time points.

^j Clinical laboratory specimens (Section 10.6.2) will be obtained at pre-dose, if study drug administration occurs on the marked study days.

^k On Days 1 and 7, PK blood draw will be performed at pre-dose and 0.25, 0.5, 1, 2, 3, 4, 6, 8, 10, 12, 16, and 24 hours post-dose. The 24-hour post-dose PK plasma samples for Days 1 and 7 should be taken before dosing on Days 2 and 8, respectively. On Days 3 to 6 and 9 to 13, PK blood draw will be performed at pre-dose only. On Day 14, PK blood draw will be performed at pre-dose and 0.25, 0.5, 1, 2, 3, 4, 6, 8, 10, 12, 16, 18, 24, 36, 48, 60, and 72 hours post-dose following the final dosing (Section 10.3.1). See Table 8 for PK time window.

^l PGX samples (whole blood) will only be collected from the subjects who consented for DNA testing.

^m Details regarding study drug administration are provided in Section 9.3.

BMI: body mass index; C-SSRS: Columbia-Suicide Severity Rating Scale; ECG: electrocardiogram; FU: Follow-up; HbsAg: hepatitis B surface antigen; HCV Ab: hepatitis C antibody; HDL: high density lipoprotein; HIV Ab: human immunodeficiency virus antibody; ICF: informed consent form; LDL: low density lipoprotein; PK: pharmacokinetic(s); PGX: pharmacogenomic(s).

TABLE OF CONTENTS

PROTOCOL AMENDMENTS	4
Amendment 1	4
Amendment 2	15
Amendment 3	17
1. PROTOCOL SYNOPSIS	19
2. SCHEDULE OF ASSESSMENTS.....	22
TABLE OF CONTENTS.....	31
LIST OF TABLES	36
LIST OF FIGURES	37
3. LIST OF ABBREVIATIONS.....	38
4. INTRODUCTION	43
4.1. Background.....	43
4.1.1. Nonclinical Experience.....	44
4.1.1.1. Pharmacology	44
4.1.1.2. Pharmacokinetics.....	46
4.1.1.3. Nonclinical safety	48
4.1.2. Clinical Experience.....	50
4.2. Rationale for Present Study	50
4.2.1. Study Design Rationale	50
4.2.2. Dosing Rationale	51
5. STUDY OBJECTIVES	54

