7. STUDY DESIGN

7.1. Overview of Study Design

This is a two-part, double-blinded, randomized study of SKL24741. The schematic of study design is shown in [Figure 1](#). [Table 4](#) further outlines the study design.

Part A is a single-dose escalation study in healthy male subjects, except for the gender effect cohort in healthy female subjects. It is expected that a total of 66 subjects (60 male and 6 female subjects) will be enrolled in Part A. Each subject will be given a single oral dose of study drug capsule (SKL24741 or placebo) on one occasion. There will be 6 new subjects at each dose level (4 subjects randomized to SKL24741 and 2 to placebo) during single-dose escalation. Study drug will be administered under fasting condition, except for one cohort utilized for the food effect assessment at one of the dose levels.

To evaluate the magnitude of the food effect on the disposition of SKL24741, a cohort of subjects will receive a second dose of study drug under fed condition (Period 2) at an appropriate dose level based on PK results. After completing Period 1 (fasting) as part of single dose escalation, these subjects will return to the clinical research unit (CRU) for a second confinement to receive a second single dose (same dose level) of study drug under fed condition. A washout period of at least 14 days is planned between fasting and fed cohorts (i.e., between Period 1 and Period 2). As subjects complete the Follow-up visit of Period 1 and then return to the CRU for re-admission (Day -1 of Period 2), the same study procedures will apply again (including Day -1 procedures) in order to initiate Period 2.

To assess the gender effect on the disposition of SKL24741, a set of 6 female subjects of non-childbearing potential will be treated at one dose level under fasting condition.

At each dose level, except for the food and gender effect cohorts, a sentinel dosing strategy will be used as described in Section [7.2](#).

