Part B is a multiple-dose escalation study in 32 healthy male subjects. Doses, dosing regimen, and food status (fasting vs. fed) used in Part B will be determined based on the outcome of Part A. Dosing will extend over a 14-day period at each dose level. Four dose levels will be assessed, and subjects will be randomized into one of the four dose levels. Each dosing cohort will have 8 new subjects (6 subjects randomized to SKL24741 and 2 to placebo) dosed each day for 14 days ([Table 4](#)). Daily dose level in Part B will not exceed the maximum dose level used in Part A.

At each dose level, a sentinel dosing strategy will be used as described in Section [7.2](#).

Table 4: Study Design

Part A: Single Ascending Doses (SAD)			
Total Number of Subjects	Randomized Stratification (Active/Placebo)	Number of Subjects per Cohort	Food Status (Fasting/Fed)
60 Male Subjects	10 mg SKL24741/Placebo	4 SKL24741/ 2 Placebo	Fasting

	25 mg SKL24741/Placebo	4 SKL24741/ 2 Placebo	Fasting
	50 mg SKL24741/Placebo	4 SKL24741/ 2 Placebo	Fasting
	100 mg SKL24741/Placebo	4 SKL24741/ 2 Placebo	Fasting
	200 mg SKL24741/Placebo	4 SKL24741/ 2 Placebo	Fasting
	300 mg SKL24741/Placebo	4 SKL24741/ 2 Placebo	Fasting
	400 mg SKL24741/Placebo	4 SKL24741/ 2 Placebo	Fasting
	600 mg SKL24741/Placebo	4 SKL24741/ 2 Placebo	Fasting
	800 mg SKL24741/Placebo	4 SKL24741/ 2 Placebo	Fasting
	1000 mg SKL24741/Placebo	4 SKL24741/ 2 Placebo	Fasting

Part A: Food Effect Assessment

Total Number of Subjects	Dose	Number of Subjects per Cohort	Food Status (Fasting/Fed)
6 Male Subjects*	Based on the outcome of Part A	6 SKL24741	Fed

Part A: Gender Effect Assessment

Total Number of Subjects	Dose	Number of Subjects per Cohort	Food Status (Fasting/Fed)
6 Female Subjects (non-childbearing potential)	Based on the outcome of Part A	6 SKL24741	Fasting

Note:

- All doses are in a capsule formulation.
- Subjects will remain in the clinic for a 4-night stay (discharged on Study Day 4).
- A sentinel dosing strategy (Section 7.2) will be used for all cohorts, except for food and gender effect cohorts, in Part A.

* Refer to Section 7.1 regarding the subjects returning to the CRU for the food effect assessment.

Part B: Multiple Ascending Doses (MAD)

Total Number of Subjects	Randomized Stratification (Active/Placebo)	Number of Subjects per Cohort	Food Status (Fasting/Fed)
32 Male Subjects	SKL24741 Dose 1/Placebo	6 SKL24741/2 Placebo	Based on the outcome of Part A

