- No fluids except those required for breakfast and dose administration will be allowed for two hours before and two hours after dose administration.

Part B – Multiple Dose Administration:

Subjects will be dosed each day for 14 days. Doses, dosing regimen, and food status (fasting vs. fed) will be based on the outcome of Part A.

In both Part A and Part B, study drug administration instructions are as follows:

- Study drug will be administered only after the indwelling catheter is placed (if applicable) and after pre-dose vital signs, peak expiratory flow rate (PEFR), and ECG are performed,
- In Part B, study drug will be given at approximately the same time (within a 1-hour window) on each dosing occasion,
- Study drug will be given as an oral capsule. Subjects will receive the study drug in an upright position. Subjects will be instructed not to lie down for 4 hours after taking the study drug, with the exception of study-specific events or assessments (sitting in an upright or reclining position [at least 45 degrees] is acceptable),
- The investigator (or his/her designee) will supervise dosing and conduct a mouth inspection of each subject to ensure that the study drug was taken.

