10.6.4.1. Safety 12-Lead ECGs

Standard 12-lead ECGs should be performed at the time points indicated in [Table 1](#) and [Table 2](#), in addition to any other times, if clinically indicated. The following guidelines must be followed:

- The subject will be instructed to rest in the supine position for at least 5 minutes before having an ECG performed,
- The ECG will be performed prior to any other procedures that may affect heart rate (e.g., blood draws).

The ECG data traces will be made for safety review by the investigator and maintained with source documentation. Any clinically significant ECG abnormalities at screening will exclude the subject's participation in the study. Thereafter, clinically significant abnormal findings will be reported as adverse events.

To ensure safety of the subjects, the Principal Investigator or designee will make comparisons to Day -1 (baseline) measurements. If the QTc is increased by >60 msec from the Day 1 pre-dose value or an absolute QTc value is >500 msec for any scheduled ECG, 2 additional ECGs will be collected, approximately 2 to 4 minutes apart, to confirm the original measurement. If either of the QTc values from these repeated ECGs remain above the threshold value (>60 msec increase from the Day 1 pre-dose; or is >500 msec), a single ECGs must be repeated at least hourly until QTc values from 2 successive ECGs fall below the threshold value that triggered the repeat measurement.

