10.6.4.2. Extensive Triplicate ECGs

Extensive triplicate 12-lead ECGs, except for the food effect cohort, will be obtained to collect continuous 12-lead ECG data from pre-dose until 24 hours post-dose at the specified time points ([Table 1](#) and [Table 2](#)). Triplicate 10-second, 12-lead ECG recordings (digital ECGs) will be obtained within a 5-minute time window around the targeted time points outlined in the Schedule of Assessments described in [Table 1](#) for Part A (single dose administration) and [Table 2](#) for Part B (multiple dose administration). During the extensive triplicate 12-lead ECG assessment, meal intake should be avoided within 1 hour of ECG data collection.

Timing and recording technique for ECGs will be standardized for all subjects. Subjects will be required to lie quietly in a supine position with minimal movement and minimal exposure to noise and other environmental stimuli for at least 5 minutes before the ECG time point in order to allow for quality ECG data. All ECG data should occur in a 5-minute time window around the targeted time. If digital ECGs are artifactual and of poor quality, analyzable 10-

second ECGs will be repeated as close as possible to targeted time points. Actual time of the ECG recording will be used for the analysis.

The triplicate 10-second, 12-lead ECG time points post-dose are guided by PK animal data and are based around the estimated T_{max} . The time points may be changed depending on PK information obtained during the study from previous cohorts.

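### In fed Period 2 of Part A no post-dose ECG is scheduled until Day 3, so neither limb of the QTc trigger in 10.6.4.1 can act during absorption and peak exposure

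*Protocol*

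**What the plan says.** Four parts of the Protocol bear on this.

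- **Schedule.** In Table 1 (Section 2) the row "Safety Single 12-Lead ECG" is marked at screening, Day -1, Day 3, Day 4 and follow-up, and is blank on Days 1 and 2. Those two days are covered only by the triplicate row.
- **Exemption.** Footnote i and Section 10.6.4.2 both remove the food effect cohort from the triplicates; the former reads "Extensive triplicate ECGs, except for the food effect cohort, will be obtained to collect continuous 12-lead ECG data from pre-dose until 24 hours post-dose" and the latter "Extensive triplicate 12-lead ECGs, except for the food effect cohort, will be obtained". Nothing is put in their place.
- **Period 2.** Section 7.1 says that after re-admission "the same study procedures will apply again (including Day -1 procedures) in order to initiate Period 2", so the Part A schedule governs the fed dose.
- **QTc rule.** Section 10.6.4.1 calls for confirmatory ECGs if QTc is "increased by >60 msec from the Day 1 pre-dose value or an absolute QTc value is >500 msec for any scheduled ECG". The sentence before it has the investigator compare with Day -1, which it calls baseline.

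Section 9.3, in instructions for both parts and with no exception for the food effect cohort, says drug is "administered only after the indwelling catheter is placed (if applicable) and after pre-dose vital signs, peak expiratory flow rate (PEFR), and ECG are performed". It gives neither the type nor the time of that ECG.

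**The concern.** The rule in 10.6.4.1 is the protocol's only numerical QTc action rule, and it depends on scheduled recordings. In the fed period there are none from dosing until Day 3. A rise or an absolute value above the threshold near peak concentration would be seen only if the investigator chose to record an ECG.

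ECG is a named component of the primary safety endpoint (6.1), and measuring the effect of food on human exposure is the purpose of this period, so that effect is unknown when the dose is given. The food effect cohort also has no sentinel dosing (7.2). There is an analysis consequence too: 11.4.4.3 tabulates the maximum on-treatment QT/QTc by category, and for fed dosing the scheduled values behind that maximum would all come from Day 3 or later.

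**Working it through.** No sample-size or power figure is involved. The check reads the schedule and counts.

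**1. ECGs scheduled in fed Period 2**
- Safety ECG row from re-admission on: Day -1, Day 3, Day 4, follow-up = 4.
- Triplicate row: exempt = 0.
- Day 1 pre-dose: 0. Day 1 post-dose: 0. Day 2: 0.

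The other Part A cohorts have triplicates at 3 pre-dose times (-0.75, -0.5, -0.25 h) and 9 post-dose times (0.5, 1, 2, 3, 4, 6, 8, 12, 24 h), 12 in all.

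**2. How late is the first post-dose ECG?** Table 1 gives no clock time for Day 3. Taken at the hour of dosing it is 2 × 24 = 48 h. With morning dosing (before noon), Day 3 cannot begin earlier than 12 + 24 = 36 h after the dose. Either way it falls after the whole 0.5 to 24 h span that 10.6.4.2 says was placed around the estimated t_max.

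**3. What the trigger can use**

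| Limb | Needs | Available in Period 2 before Day 3 |
|---|---|---|
| >500 msec | a scheduled ECG | none after dosing |
| >60 msec rise | a scheduled ECG and a Day 1 pre-dose value | no ECG after dosing; reference unclear |

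**4. The reference.** Three provisions do not agree:
- 9.3 makes a pre-dose ECG a condition of dosing.
- Table 1 with footnote i schedules no Day 1 ECG for this cohort.
- 10.6.4.1 names Day -1 as baseline, then measures the 60 msec rise from Day 1 pre-dose.

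A Day -1 safety ECG does exist in Period 2, and the same subjects have a Period 1 Day 1 pre-dose triplicate. The protocol does not say that either one stands in for the Period 2 Day 1 value.

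**5. Does the meal rule explain the gap?** Breakfast starts about 0.5 h before dosing and is eaten in 30 minutes or less, so it runs from -0.5 h to at most 0 h. One hour either side gives -1.5 h to 1 h. That covers -0.75, -0.5, -0.25 and 0.5 h, 4 of the 12 triplicate times, with 1 h on the limit. The other 12 - 4 = 8 times are not inside the breakfast window. Lunch at 4 to 5 h (8.3.1) touches the 4 h point, but it does so in every cohort. The meal rule may justify dropping the early triplicates; it does not explain having no ECG later on Day 1 or on Day 2. Table 8 already gives the fed pre-dose PK sample its own slot before breakfast; the ECG has none.

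**The case against.** The strongest reply is that the exemption is deliberate and the risk small. Much of this stands.

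- The exemption appears twice, and the food-effect objective concerns PK only. That supports dropping the triplicates, but not leaving a safety rule with nothing to act on.
- Under 7.2 the dose must first be judged acceptable under fasting, where triplicates are taken. Fed and fasted rats had similar exposure (4.1.1.2), and dog telemetry showed shorter QTc, by up to 9 msec (4.1.1.1).
- Human exposure is capped at the rat NOAEL, C_max 3.32 µg/mL (4.2.2). The structure in 4.1 gives C18H15F3N2O2, molecular weight about 348, so the cap is 3.32 / 348 × 1000 ≈ 9.5 µM total. At about 96% human binding, 9.5 × 0.04 ≈ 0.38 µM is free. Against a hERG IC50 of 21.1 µM the margin is 21.1 / 0.38 ≈ 55-fold, or about 28-fold if exposure doubled.
- The trigger only starts repeat ECGs; it is not a stopping rule. Subjects are confined, have 7 post-dose vital-sign sets on Day 1 (1, 2, 3, 4, 6, 8, 12 h), and may have extra ECGs at the investigator's discretion (10.6.4). Discretion is not a schedule, and vital signs do not measure QTc.

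Two stronger readings are tempting.

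A reader might infer that the >60 msec limb has no reference at all. The documents do not support that: 9.3 demands a pre-dose ECG, and Day -1 is recorded and called baseline. The fault is a conflict between provisions.

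A reader might also infer that two of the six fed subjects receive their first active dose, since the fasting cohort has "4 subjects randomized to SKL24741 and 2 to placebo" while Table 4 lists all six fed subjects on SKL24741. But 7.1 describes the fed dose as a second administration of study drug at the same level, and there study drug means active or placebo. The text does not settle this, and the conclusion here does not rest on it.

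**Conclusion.** The gap is real. Fed Period 2 has 4 scheduled ECGs, none on Days 1 or 2, and the first after dosing is on Day 3 (nominally 48 h, assuming it is taken at the hour of dosing). Neither limb of the 10.6.4.1 trigger can act on a scheduled ECG during absorption and peak exposure. This rests on Table 1, footnote i, 10.6.4.2 and 7.1, which agree with each other. Separately, 9.3, Table 1 and 10.6.4.1 are inconsistent on the pre-dose reference.

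The protocol's own data point to low risk, and nothing in the documents demonstrates a QT hazard. This is a worthwhile, inexpensive correction to a safety rule, not a defect that endangers the study or its conclusions.

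**What to change.** In Table 1, add single safety 12-lead ECGs for the food effect cohort in Period 2:

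- Day 1 before breakfast, which gives the ECG that 9.3 already requires a time;
- one or two times on Day 1 near the t_max seen in the fasting cohorts, more than 1 hour from meals;
- 24 h (Day 2).

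In 10.6.4.1, state that the >60 msec limb uses the Day 1 pre-dose ECG of the same period, and what the Day -1 comparison is for.

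Cost: 1 + (1 or 2) + 1 = 3 or 4 ECGs per subject. For six subjects that is 6 × 3 = 18 to 6 × 4 = 24 recordings, of which 6 are the pre-dose ECGs already called for in 9.3. The subjects are confined and the equipment is in use. Triplicates need not be restored, and no dose, sample size or PK time changes.
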